8.5. Medical Resource Utilization

As of Amendment 7, this is no longer applicable.

Medical resource utilization data over the last 3 months, associated with medical encounters, will be collected by interview with the participant and recorded in the eCRF by the investigator and study-site personnel at baseline (for all participants, concerning MRU within the last 3 months before 1st vaccination), and on COVID-19 Day 3-5 and COVID-19 Day 29 (for all participants during a COVID-19 episode; which is defined to be resolved after having 2 consecutive SARS-CoV-2 negative nasal swabs and 2 consecutive days with no COVID-19-related signs or symptoms; see Section 8.1.2]) ([Appendix 7](#)).

Medical resource utilization data will also be collected through the MA-COV form ([Appendix 8](#)). This form will be provided to the participant at the 1st vaccination visit and should be completed by the medical care provider or the study site personnel during medical visits for COVID-19 or COVID-19 complications. Protocol-mandated procedures, tests, and encounters are excluded. The data collected may be used to conduct exploratory economic analyses and will include:

- Number and duration of medical care encounters, including selected procedures (inpatient and outpatient)
- Duration and type of mechanical ventilation and ECMO use
- Duration of hospitalization (total days length of stay, including duration by wards; eg, ICU)
- Number and character of diagnostic and therapeutic tests and procedures
- Outpatient medical encounters and treatments (including physician or emergency room visits, tests and procedures, and medications)

8.6. Risk Factor Assessment

As of Amendment 7, this is no longer applicable.

If allowed by local regulations and if the participant consents, he/she will be interviewed on characteristics related to his/her current work situation, living situation, and community interactions (See [Appendix 12](#)) prior to vaccination on Day 1 and at other timepoints, on changes compared to Day 1. These characteristics can potentially be useful to identify the risk of individual participants in acquiring COVID-19 and will be used in several analyses including correlate analysis.

Risk factor data initially collected at screening from the participants, prior to implementation of the Protocol Amendment 2 will also be used for the planned risk-factor analysis.

8.7. Participant Medical Information Prior to, During and After the Study (Real-world Data)

In the US, for consenting participants, medical data from 5 years prior to study enrollment until 5 years after study completion, such as electronic health records, claims and laboratory data from other care settings, may be accessed utilizing tokenization and matching procedures. These data together with data collected as part of the study as specified in the [Schedules of Activities](#), may be used to conduct exploratory analyses to enhance our understanding of the impact of prior medical history on the response to immunization and the impact of immunization on efficacy and duration of efficacy as well as adverse events that may occur during and after completion of the study (see Section [9.4.4](#)). The utilization of tokenization and matching procedures allows for the medical data to be obtained without violation of participant confidentiality (Sections [4.2](#) and [4.2.1](#)). The real-world medical data, which are not collected as part of the study, will not be part of the clinical study database.

8.8. Assessment and Procedures After Emergency Use Authorization and Implementation of Protocol Amendment 4

Following Ad26.COV2.S EUA in the US for the single dose schedule based on the VAC31518COV3001 study interim results, all participants from countries where Protocol Amendment 4 is approved by the local Health Authority and IEC/IRB will be unblinded. The study will then be conducted in an open-label fashion. Before the actual participant unblinding, all of the previously available data should be complete and accurate in the participant's eCRF.

All participants that have not discontinued prematurely from the study will have an unblinding visit at which they will be reconsented (Schedule of Activities [1.3.4](#)). This visit is also applicable for participants who were already unblinded during the double-blind phase of the study. If applicable, participants will receive a single dose of Ad26.COV2.S (refer to Section [6.4](#) for participants enrolled in the study during the double-blind phase). At this visit, body temperature, a blood sample, and a nasal swab will be collected from all participants.^a The nasal sample will not be tested locally and will be sent to a central laboratory. A urine pregnancy test (for participants of childbearing potential) will be collected from participants who will be vaccinated with a single dose of Ad26.COV2.S at this visit. If the participant receives a single dose of Ad26.COV2.S at this visit, the above-mentioned procedures will be performed before vaccination.

After vaccination, participants should remain under observation at the study site for at least 15 minutes, except where local regulations require a longer observation period (eg, Belgium), for the presence of any acute reactions after vaccination and will be followed for safety as per

^a The unblinding visit may be combined with the scheduled study visit and procedures that would be duplicated should be done only once. If a blood draw is planned in the scheduled visit no additional blood draw is needed.

Section 8.3. After the unblinding visit, all participants will resume the Schedule of Activities from Section 1.3.3.

The unblinding visit can be done at an already scheduled or an unscheduled visit. Preferably, if a scheduled study visit (Schedule of Activities 1.3.3) is planned within 2 months after the receipt of Amendment 5 local approvals, this unblinding visit may be combined with the planned study visit. If the unblinding visit is combined with a scheduled visit, the procedures of the planned visit should be completed as well with the exception of solicited symptoms collection in the Safety subset (See Section 8.3). If a blood sample is already planned for the scheduled visit, the blood sample of the unblinding visit does not need to be collected.

Participants initially enrolled in the Ad26.COV2.S group during the double-blind phase who will not receive a second vaccination (refer to Section 6.4) will be assured they received the dose level that was submitted for EUA (single-dose schedule of 5×10^{10} vp Ad26.COV2.S), and will be asked to continue to be followed in this study in line with the Schedule of Activities Section 1.3.3.

Investigators will be encouraged to follow health authority guidelines on prioritization of immunization. Investigators are encouraged to consider current local public health guidance for determining the scheduling priority of participants. For example, participants with comorbidities and/or of specific age groups can be scheduled prior to participants without comorbidities if this is in line with local guidance. This should be done in a blinded way, ensuring that participants who were not previously unblinded for other reasons are not unblinded until the unblinding visit. All participants will be counselled to continue practicing other public health/preventive measures that were introduced at the start of this pandemic (eg, social distancing, face masks, frequent hand washing), in compliance with local and national guidelines.

8.9. Assessment and Procedures for Booster Vaccination and Follow-up After Implementation of Protocol Amendment 6

As of Protocol Amendment 7:

No further booster doses will be administered after implementation of Protocol Amendment 7, except if there is a medical reason or if there is a non-availability of other vaccines to the participant. The investigator should inform participants on the availability of other COVID-19 vaccines.

Up to Protocol Amendment 7:

With implementation of Protocol Amendment 6, all ongoing participants who received only a single vaccination with Ad26.COV2.S in the study will be offered a single booster dose of Ad26.COV2.S vaccine under the conditions delineated in Section 6.5. Participants who already received 2 vaccinations with Ad26.COV2.S at the 5×10^{10} vp dose level or any COVID-19 vaccinations outside of the study (including the Janssen vaccine) at the time of local approval of Protocol Amendment 6 are not eligible to receive a booster vaccination with Ad26.COV2.S.

Eligible participants who consent to receive the booster vaccination will follow the schedule as presented in Section 1.3.5. The following assessments will be performed before booster

vaccination: measurement of body temperature, check of pre-vaccination symptoms (see Section 5.5), a urine pregnancy test (women of childbearing potential only), a nasal sample collection for SARS-CoV-2 testing, a blood sample for humoral immunogenicity and SARS-CoV-2 serology, and a clinical lab blood sample^a (for platelet count, as part of a complete blood count, if applicable). After receiving the booster vaccination, participants should remain under observation at the study site for at least 15 minutes, except where local regulations require a longer observation period (eg, Belgium), for the presence of any acute reactions after vaccination and will be followed for safety as per Section 8.3. Concomitant therapies will be recorded as per Section 6.10.

The booster vaccination will be administered in the open-label phase of the study, preferably within 6 to 12 months after the participant's first Ad26.COV2.S vaccination in the study. If this is not possible, the booster vaccination should not occur earlier than 3 months after the participant's first Ad26.COV2.S vaccination. The Booster Vaccination Visit should preferably coincide with the participant's next scheduled visit (ie, Visit 7 or Visit 8 for the majority of participants) from the original SoA in Section 1.3.3. If not operationally feasible to coincide with an existing visit, an unscheduled visit may be planned. If the Booster Vaccination Visit coincides with a scheduled visit, the procedures of the scheduled visit should be completed as well. However, procedures that would be duplicated should be done only once. If a whole blood sample has been taken within 5 days before vaccination and platelet results are available, sample collection does not need to be performed before vaccination.

After the Booster Vaccination Visit, participants will continue procedures and visits as in the original SoA. All participants (whether they consent to the booster vaccination or not) will be encouraged to remain in the study and will be monitored for safety, immunogenicity, and efficacy according to their original schedule.

Investigators will be encouraged to follow health authority guidelines on prioritization of immunization. Investigators are encouraged to consider current local public health guidance for determining the scheduling priority of participants. For example, participants with comorbidities and/or of specific age groups can be scheduled prior to participants without comorbidities if this is in line with local guidance. All participants will be counselled to continue practicing other public health/preventive measures that were introduced at the start of this pandemic (eg, social distancing, face masks, frequent hand washing), in compliance with local and national guidelines.

^a Whole blood samples will be used for immediate measurement of a platelet count (as part of a complete blood count if applicable) in a local laboratory or substitute for local laboratory, depending on local feasibility towards turnaround time of sample processing. Serum samples will be derived from the whole blood sample and stored for potential future coagulation-related testing in a central laboratory if the participant experiences a suspected AESI (see Section 10.2, Appendix 2).

9. STATISTICAL CONSIDERATIONS

Statistical analysis will be done by the sponsor or under the authority of the sponsor. A general description of the statistical methods to be used to analyze the efficacy and safety data is outlined below. Specific details will be provided in the SAP.

Sections 9.2 to 9.6 are applicable to the double-blind phase of the study. Considerations for the analysis of the open-label active phase and the open-label passive follow-up phase (introduced with Amendment 4 to Amendment 7) of the study are described in Section 9.7; details will be provided in a separate SAP.

9.1. Statistical Hypotheses

Refer to Section 3 for the statistical hypotheses.

The study will have 3 timepoints for analysis:

1. The primary efficacy analysis of the double-blind phase is planned to be performed when all participants have reached the open-label phase/been unblinded. Depending on the operational implementation of unblinding visits, as well as the stage of the pandemic, the analysis may be conducted when a minimum of 90% of the study population have reached the open-label phase/been unblinded.

After the primary analysis, additional analyses to support health authority interactions may be planned, if deemed appropriate.

During the open-label phase, 2 analyses can be performed:

2. The open-label active phase analysis
3. An end-of-study analysis is planned 1 year after a minimum of 90% of the enrolled study population have reached Visit 8 or discontinued earlier and will be conducted upon completion of the last active participant visit. Depending on the timing of approval of Amendment 7 across study sites, the open-label active phase analysis may be combined with the end-of-study analysis. All boosted participants will have at least 6 months safety follow-up.

Additional analyses may be conducted to support health authority interactions and/or based on public health demand in case of emerging variants.

9.2. Sample Size Determination

9.2.1. Efficacy (Total Sample Size)

For the double-blind phase, the sample size is determined using the following assumptions:

- a VE for molecularly confirmed, moderate to severe/critical SARS-CoV-2 infection of 65%.
- type 1 error rate $\alpha = 2.5\%$ to evaluate VE of the vaccine regimen.
- a randomization ratio of 1:1 for active versus placebo

Events are defined as first occurrence of molecularly confirmed, moderate to severe/critical COVID-19 according to the case definition in Section 8.1.3.1 in the PP population at least 14 days after the second vaccination with study vaccine (Day 71).

Under the assumptions above, a total of 104 events will provide approximately 90% power to reject the null hypothesis of $H_0: VE \leq 30\%$, according to the primary endpoint case definition of moderate to severe/critical COVID-19 (Section 8.1.3.1).

If the primary hypothesis testing is successful, secondary objectives will be evaluated against a null hypothesis employing a lower limit $VE > 0\%$. The method to perform hypothesis testing of primary and secondary objectives preserving the FWER will be specified in the SAP. The FWER will be controlled at 2.5%.

Sample Size Justification

Based on the variations in seroprevalence, degree of social distancing and use of personal protective equipment, it is not feasible to estimate the incidence rates that can be attained at the time of the start of this study. It is also unknown which local regulations (eg, potential lockdowns) will be in effect at that time.

The sample size is approximately 15,000/group (approximately 30,000 in total) and is determined based on estimated annualized incidence rate of moderate to severe/critical COVID-19 of 1% to 4% at the start of the study.

Assuming 2 months of recruitment and 10% seroprevalence, the selected sample size will have a high probability (approximately 90%) to have reached an efficacy signal within 15 months after first participant vaccinated for an assumed $VE \geq 65\%$ under an assumed incidence of 1.4% in Month 1-3, and waning of incidence thereafter, eg, 50% reduction at Month 4 (0.70% annualized) followed by further reduction to 0.58%.

With higher incidences at the start of the study, the timelines to efficacy will shorten.

The operating characteristics of the study design, statistical methods, study monitoring rules and efficacy evaluations specified in this protocol with the chosen event and sample sizes will be described in a separate modeling and simulation report and will be added to the SAP before the first participant is vaccinated. The SAP will be amended before primary analysis of the double-blind phase. Upon implementation of Protocol Amendment 6, the SAP will be amended before the next scheduled analysis.

To maximize power for the secondary objectives and evaluations in subgroups, any interim testing was abandoned, and a single analysis planned at the end of the double-blind phase.

The overall recruitment target is approximately 30,000 participants. Up to 10% of additional participants may be recruited to partially compensate for increased fraction unblinded prior to unblinding visit and/or increased seroprevalence rates and/or drop-outs.

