9.4.1. Primary Endpoint Evaluation for the Double-blind Phase

The double-blind phase of the study is designed to test the primary hypothesis of VE in the PP population: H0: VE $\leq 30\%$ versus H1: VE $> 30\%$ and will be evaluated at a 2.5% 1-sided significance level.

The primary endpoint will evaluate the first occurrence of molecularly confirmed, moderate to severe/critical COVID-19 according to the case definition in Section 8.1.3.1, with onset at least 14 days after the second vaccination (Day 71) with Ad26.COV2.S versus placebo, in the PP population, including all events from both age groups, with and without comorbidities.

Participants included in the seronegative analysis set are those participants with a negative SARS-CoV-2 serology test result at baseline.

The unblinding visit marks for a participant the end of the double-blind phase, and the start of the open-label phase. For a given participant, all data up to the unblinding visit will be incorporated in the analysis of the double-blind phase.

The minimum criteria that may trigger the primary analysis before at least 90% of participants are unblinded is if the prespecified harm boundaries have been crossed.

A successful primary efficacy conclusion will require establishing the hypothesis H1: VE $> 30\%$ for the primary endpoint.

Exact Poisson regression will be used to estimate the VE and associated CI taking into account the follow-up time. To evaluate the primary null hypothesis: H0: VE $\leq 30\%$ versus H1: VE $> 30\%$ for the primary endpoint, 95% 2-sided confidence interval based on Poisson regression model will be used.

The decision rules for harm are detailed in Section 9.4.1.1.

For any case definition to be considered for classification of COVID-19 cases, there needs to be at least one SARS-CoV-2 positive RT-PCR or molecular test result from any available respiratory tract sample (eg, nasal swab sample, sputum sample, throat swab sample, saliva sample) that is confirmed by the central laboratory. It is possible that not all samples can be confirmed at the time of the analysis. Hence, a sensitivity analysis may be performed using all RT-PCR or molecular test result, regardless of the confirmation by the central laboratory.

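### Section 9.2.1 still promises about a 90% chance of an efficacy signal within 15 months, but the primary analysis is now triggered by unblinding, which the document's own dates place at most about 12.65 months after first vaccination

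*Protocol*

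**What the plan says.** Section 9.2.1 gives two justifications of size for the double-blind phase.

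- Power at a given event count: "Under the assumptions above, a total of 104 events will provide approximately 90% power to reject the null hypothesis" of VE at or below 30%, with VE 65%, one-sided 2.5% and "a randomization ratio of 1:1 for active versus placebo".
- Probability by a given time: about 15,000 per group "will have a high probability (approximately 90%) to have reached an efficacy signal within 15 months after first participant vaccinated". This assumes 2 months of recruitment, 10% seroprevalence, VE of at least 65%, and annualized incidence of 1.4% in Months 1 to 3, 0.70% at Month 4 and 0.58% afterwards. The section also names a starting range of 1% to 4% and says that higher starting incidence shortens the timeline.

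The timing of the analysis is set elsewhere. Section 9.1 plans the primary analysis for when all participants are unblinded, and "the analysis may be conducted when a minimum of 90% of the study population have reached the open-label phase/been unblinded". Section 9.8 repeats the 90% rule. Section 9.4.1 ends each participant's double-blind data at the unblinding visit and names only a crossed harm boundary as an earlier trigger. Section 9.2.1 itself says that interim testing was abandoned in favour of one analysis at the end of the double-blind phase. Section 8.8 has participants unblinded after the US emergency authorization and local approval of Amendment 4: "The study will then be conducted in an open-label fashion". None of these sections sets a minimum number of events.

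**The concern.** The 15-month statement fits a design in which blinded follow-up continues until enough events accrue. The current design stops blinded follow-up at unblinding, whatever the count. If unblinding comes well before month 15, the stated probability is not the probability that the design delivers under the same assumptions.

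This affects how the result is read. Section 9.4.1 makes success depend on excluding VE of 30% or less, and Section 9.2.1 makes the secondary tests conditional on that success. A reader who relies on the 90% figure could take a failure to reject as evidence against the vaccine when the number of events was simply small.

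**Working it through.** **Inputs from Section 9.2.1.** 30,000 participants randomized 1:1, 10% seropositive, uniform 2-month accrual, events counted from Day 71, incidence 1.4% / 0.70% / 0.58%, VE 65%, null VE 30%, one-sided 2.5%. I assume no drop-out and one cut date for all participants.

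**Power at 104 events.** Conditional on D events, the vaccine-arm count is binomial with p = RR/(1+RR). Under the null p = 0.70/1.70 = 0.4118; under VE 65% p = 0.35/1.35 = 0.2593. At D = 104 the test rejects at 32 or fewer vaccine cases, with exact alpha 0.0187 and power 89.1%. The stated figure of about 90% reproduces.

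**Expected events by month T.** Seronegative participants per arm: 15,000 × 0.9 = 13,500. Combined yield: 13,500 × (1 + 0.35) = 18,225 placebo-equivalents. The share at risk rises linearly from month 2.30 (70 days) to month 4.30.

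- Months 2.30 to 3: 18,225 × 0.014/12 × 0.70²/4 = 2.6
- Months 3 to 4: 18,225 × 0.007/12 × 0.60 = 6.4
- Months 4 to 4.30: 18,225 × 0.0058/12 × 0.925 × 0.30 = 2.4
- After month 4.30: 18,225 × 0.0058/12 = 8.81 per month

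So E(T) = 11.4 + 8.81 × (T − 4.30). At T = 15 this gives 105.7 events. Averaging exact power over a Poisson count with that mean gives 89.5%. The stated 15-month figure also reproduces.

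**How long the blinded period can be.** Section 7.1 describes existing participants as enrolled under Amendments 1, 2 or 3, so I take first vaccination as no earlier than Amendment 1 (25 September 2020). The Amendment 6 rationale (15 October 2021) already cites this study's primary analysis. That is 385 days, or 12.65 months at most. Two shorter reference points are Amendment 4 (12 March 2021) plus 2 months, which is 229 days or 7.5 months, and Amendment 5 (6 May 2021) plus 2 months, which is 284 days or 9.3 months.

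**Same scenario, cut at those times:**

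| Months from first vaccination | Expected events | Averaged power |
|---|---|---|
| 7.5 | 40 | 46% |
| 9.3 | 56 | 62% |
| 12.65 (outer bound) | 85 | 81% |
| 15 (as stated) | 106 | 90% |

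**Other incidence levels.** With the same relative waning, events scale with the starting rate. At 9.3 months a 1% start gives 56 × 1/1.4 = 40 events; a 3% start gives about 119; a 4% start gives about 159. Without waning, a constant rate of about 1.6% at 7.5 months or 1.1% at 9.3 months is enough for 104 events.

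**Why averaged power.** Exact power at a fixed count is saw-toothed: 31 events give 42.6% and 40 events give 38.7%. Averaged over a Poisson count it is smooth: means of 40, 60, 80 and 104 give 46%, 65%, 79% and 89%.

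**The case against.** The strongest defence is that nothing in Section 9.2.1 is miscalculated. The 104-event statement is conditional and does not say that 104 events will accrue before unblinding. This stands.

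Incidence is expressly uncertain, the waning pattern is given as an example, and the text says that higher incidence shortens timelines. This also stands. A reader might infer that the trial was underpowered, but the documents do not support that without the scenario attached.

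The blinded period is not stated. The date of first vaccination is not in the part of the protocol shown, the amendment dates are document dates rather than local approvals, and the 2-month wording in Section 8.8 is a preference about combining visits. A fixed blinded period of 8 to 10 months therefore cannot be read from the text. The 12.65-month limit is firmer, and it still excludes 15 months.

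Section 9.2.1 allows up to 10% more participants. With 33,000 the figures become about 61 events and 66% at 9.3 months, and about 93 and 85% at 12.65 months, which narrows the gap without closing it.

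Operating characteristics are assigned to a simulation report and the SAP, and the SAP was to be amended before the primary analysis. It may give updated figures, but that does not correct a probability the protocol itself still states. Finally, the primary analysis has been done, so the correction changes no test, alpha level or estimate.

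**Conclusion.** The point holds in limited form. The 15-month statement no longer describes the design: the trigger is unblinding, the event count is random, and the document's dates leave at least about 2.3 months less than the 15 assumed. Under the protocol's own scenario, averaged power is about 46% to 62% at the inferred unblinding times and 81% at the outer bound, against about 90% stated.

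These figures rest on the earliest possible start, 2-month recruitment, no drop-out and a single cut date. Departures from these mostly lower them. For example, 3.5 months of recruitment gives 48 events and 55% at 9.3 months, and a start on 27 November 2020 gives 38 events and 43% at Amendment 5 plus 2 months. Higher incidence works the other way and can restore 90% or more.

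A reader might also infer that failing to reject with fewer than 104 events should automatically count as inconclusive. That cut-off has no basis: exact power is 90.2% at 103 events and 89.1% at 104. The VE estimate and its 95% confidence interval, already required by Section 9.4.1, show how much information was available.

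**What to change.** In Section 9.2.1:

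- State that the double-blind analysis is triggered by unblinding and that the number of events is therefore random.
- Keep 104 events only as a conditional reference number for about 90% power.
- Replace the 15-month sentence with expected events and averaged power at the planned unblinding time, over the 1% to 4% incidence range and with the waning assumption stated. A compact form is averaged power by expected events: 40 gives 46%, 60 gives 65%, 80 gives 79%, 104 gives 89%.
- Add no event-count rule for calling a result inconclusive; rely on the VE estimate and its 95% confidence interval.

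The cost is a change of wording and a less favourable stated power. No extra participants are needed, and the test and significance level are unchanged.
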